Inflammatory response: long-term peritoneal dialysis will cause chronic micro-inflammatory response, resulting in increased catabolic metabolism, reduced synthetic metabolism, decreased appetite, endocrine dysfunction and so on. At the same time, inflammatory response will also affect vascular permeability and hemodynamics, reducing ultrafiltration efficiency and the ability to remove toxins.

Malnutrition not only affects the quality of life of peritoneal dialysis patients, but also increases the risk of complications such as infection, cardiovascular events, and peritoneal failure, reducing survival rates. Therefore, improving the nutritional status of peritoneal dialysis patients,

It is one of the important measures to improve its prognosis and quality of life.

Currently, nutritional support strategies for peritoneal dialysis patients mainly include oral nutritional supplementation, enteral nutrition supplementation, parenteral nutrition supplementation, and modified peritoneal dialysate. Among these, modified peritoneal dialysate refers to adding beneficial components such as amino acids, ketones, and low-osmolarity agents to conventional glucose-containing peritoneal dialysate. This reduces glucose absorption, increases the clearance of water and toxins, provides essential amino acids and energy, and improves the body's metabolic function

Check your physical and nutritional status.

Amino acids are the fundamental units for protein synthesis and other important substances in the body, and they also serve as one of the key energy sources for oxidative metabolism. Amino acid peritoneal dialysate is a sugar-free and osmotic agent-free peritoneal dialysate containing 1.1% (11 g/L) free amino acids, with an amino acid composition similar to that found in human plasma. The main mechanisms of action of Amino acid peritoneal dialysis fluid are as follows: supplemental amino acids: Amino acid peritoneal dialysis fluid can provide amino acids to the blood through peritoneal diffusion, thus to compensate for the loss of protein and amino acids, increase serum albumin level, improve the body nitrogen balance and nutritional status.

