3.1 Research design

This study adopts a multicenter, open, prospective, and self-controlled design, where each participant serves as their own control before and after receiving amino acid peritoneal dialysis fluid treatment, to compare changes in their nutritional status. This study does not set up a placebo or control group, as amino acid peritoneal dialysis fluid is already on the market, with its efficacy and safety proven, and there are no equivalent alternatives. The primary objective of this study is to observe the nutritional improvement effects and safety assessment of amino acid peritoneal dialysis fluid for malnourished peritoneal dialysis patients. Specific techniques

The route is shown in Figure 1:

[figure not shown]

Figure 1. Technical route

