3.2 Study endpoints and evaluation criteria

3.2.1 Main end indicators

The primary endpoint of this study was the improvement of nutritional status of subjects after 3 months and 6 months of treatment, it includes the following two indicators:

- 1) Serum albumin (g/L): the change value of serum albumin compared with baseline at 3 months and 6 months after treatment (Δ serum albumin);
- 2) Prealbumin (mg/L): the change value of prealbumin at 3 months and 6 months after treatment. The change value of prealbumin compared with the baseline after month (Δ prealbumin); The treatment was considered effective if the difference in change from baseline for any of the above indicators was statistically significant.

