The daily use of 1 bag of amino acid peritoneal dialysis fluid is during the nighttime sleep period, while the daily use of 2-4 bags of glucose peritoneal dialysis fluid is during the daytime. The total daily infusion volume, each infusion volume, dwell time, and each excretion volume for each subject are adjusted by the researcher based on individual patient conditions and standardized prescriptions. During treatment, subjects should follow the researcher's guidance for daily life and dietary management, and regularly visit the research center for follow-up and examinations. In the third and sixth months of treatment, subjects should repeat the screening period

All evaluation items and any adverse events or serious adverse events are recorded.

The research process is shown in Table 1:

Table 1: Research process table

Evaluate projects	Screening period/baseline	stage of therapy					
		1 month	2 months	3 months	4 months	5 months	6 months
informed consent	√	×	×	×	×	×	×
Inclusion and exclusion criteria	√	×	×	×	×	×	×
Collect demographic data	√	×	×	×	×	×	×
Symptoms (loss of appetite, nausea, vomiting, abdominal distension, Infusion pain, edema, etc.)	√	√	√	√	√	√	√

Previous illness/treatment	✓	✗	✗	✗	✗	✗	✗
Combination therapy with concomitant medication	✓	✓	✓	✓	✓	✓	✓
allergic history	✓	✗	✗	✗	✗	✗	✗
SGA	✓	✓	✓	✓	✓	✓	✓
check-up	✓	✓	✓	✓	✓	✓	✓
vital sign	✓	✓	✓	✓	✓	✓	✓
Ultrafiltration volume	✓	✓	✓	✓	✓	✓	✓
UPD	✓	✓	✓	✓	✓	✓	✓
BMI	✓	✓	✓	✓	✓	✓	✓
CI	✓	✗	✗	✓	✗	✗	✓
skin-fold thickness	✓	✗	✗	✓	✗	✗	✓
Waist circumference and grip strength, upper arm muscle circumference	✓	✗	✗	✓	✗	✗	✓
Hepatitis B related antigen antibody, hepatitis C antibody, HIV antibody	✓	✗	✗	✗	✗	✗	✗
Biochemistry and liver and kidney function (including serum albumin, Prealbumin), glycosylated hemoglobin	✓	✗	✗	✓	✗	✗	✓
White, fasting blood sugar							
Nt-Pro BNP	✓	✗	✗	✓	✗	✗	✓
nPCR	✓	✗	✗	✓	✗	✗	✓

nPNA	✓	✗	✗	✓	✗	✗	✓
Kt/V and Ccr	✓	✗	✗	✓	✗	✗	✓
PET	✓	✗	✗	✓	✗	✗	✓
adverse event	✓	✓	✓	✓	✓	✓	✓

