5.1.2 Treatment dose adjustment

During the treatment, according to the changes of the patient's ultrafiltration volume, blood pressure, biochemical blood, nutritional status and other indicators, the researchers can adjust the dosage and frequency of treatment appropriately to ensure the patient's water and electrolyte balance and metabolic stability. Specifically, the adjustment principles are as follows:

If the patient develops signs of water retention such as weight gain, edema, and hypertension, the researcher can increase the frequency of amino acid peritoneal dialysis or increase the concentration of glucose peritoneal dialysis to increase ultrafiltration and reduce water Sub-daily intake.

If the patient shows signs of water loss such as weight loss, hypotension, and hypoglycemia, the researcher can reduce the number of times of amino acid peritoneal dialysis fluid or reduce the concentration of glucose peritoneal dialysis fluid to reduce the amount of ultrafiltration and increase water intake.

If the patient shows signs of elevated or decreased blood potassium, the investigator can administer drug therapy to replenish potassium, to maintain normal blood potassium levels. If the patient shows signs of elevated or decreased blood calcium, the investigator can adjust the patient's calcium and vitamin D. The dosage of the drug is to maintain the blood calcium level within the normal range.

If the patient shows a decrease in nutritional indicators such as serum albumin, prealbumin, nPCR, and nPNA, the researcher can increase the number of times or volume of amino acid peritoneal dialysis to provide more amino acids and energy, and give patients appropriate nutritional support and education.

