5.2 Adjuvant therapy/combined medication

During treatment, in addition to the use of amino acid peritoneal dialysis fluid and glucose peritoneal dialysis fluid, the subjects should also

Continue with their original adjuvant therapy, including:

Nutritional support drugs: if the patient has been taking nutritional drugs before entering the study, continue the original nutritional drug treatment,

No additional nutritional support drugs were added after entering the study.

Antihypertensive drugs: adjust the type of antihypertensive drugs according to the patient's blood pressure level and ultrafiltration. The dose is used to keep blood pressure within the target range.

Antianemia drugs: erythropoietin is adjusted according to the patient's hemoglobin level and iron metabolism. The type and dose of EPO and iron supplements were used to improve anemia.

Calcium and vitamin D drugs: according to the patient's blood calcium, blood phosphorus, parathyroid hormone (PTH) and other indicators

Targets, adjust the types and doses of calcium and vitamin D drugs to prevent and treat renal bone disease.

Phosphorus binder: Adjust the type and dose of phosphorus binder according to the patient's blood phosphorus level and diet. Control blood phosphorus levels within the target range.

Anticoagulant drugs: adjust the type and dose of anticoagulant drugs according to the patient's coagulation function to prevent and treat thrombosis.

Other drugs: other necessary drug therapy, such as anti-infective drugs, is given according to the specific condition of the patient anti-heart failure drugs, anti-arrhythmia drugs, uric acid reduction.

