5.3 Treatment compliance

During the treatment period, participants should use the amino acid peritoneal dialysate and glucose peritoneal dialysate correctly according to the instructions and prescriptions of the researcher, and record each infusion volume, retention time, and output. Participants should submit their daily treatment logs to the researcher for verification and storage. Participants should maintain good peritoneal dialysis techniques and hygiene habits to prevent infections and complications. Participants should regularly visit the research center for follow-up visits and examinations, and promptly report any adverse reactions or discomforts to the researcher. Participants should adhere to dietary, hydration, and exercise recommendations provided by the researcher and avoid using other drugs or treatments that may affect the results of this study. If a participant is unable to continue participating in this study for any reason, they should notify the researcher in a timely manner and explain the reasons for withdrawal follow.

6. Adverse events

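### Section 5.1.2 lets a fall in a primary endpoint prompt undefined nutritional support; with no control group and no analysis that separates it, any gain would count as dialysate effect

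*Combined protocol and SAP*

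**What the plan says.** Section 5.1.2 sets the trigger: "If the patient shows a decrease in nutritional indicators such as serum albumin, prealbumin, nPCR, and nPNA, the researcher can increase" the number or volume of amino acid exchanges, "to provide more amino acids and energy, and give patients appropriate nutritional support and education". Two of the four named indicators, albumin and prealbumin, are the primary endpoints in 3.2.1. No size of fall, type of support or time limit is given.

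Section 5.2 keeps existing nutritional drugs and says "No additional nutritional support drugs were added after entering the study". Section 5.3 asks participants to "avoid using other drugs or treatments that may affect the results of this study", but also to follow the researcher's dietary advice. The background (section 1) says that "nutritional support strategies for peritoneal dialysis patients mainly include oral nutritional supplementation, enteral nutrition supplementation, parenteral nutrition supplementation, and modified peritoneal dialysate".

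On design, 3.1 states "This study does not set up a placebo or control group". Table 1 schedules albumin and prealbumin at baseline, month 3 and month 6. It has a row "Combination therapy with concomitant medication", ticked at every visit, and 7.6.1 counts patients by treatment category. Section 7.6.2 runs a paired t-test of month 6 against baseline in the effectiveness analysis set (EAS); its sensitivity analyses change only how missing values are filled. The success rule is in 3.2.1: "The treatment was considered effective if the difference in change from baseline for any of the above indicators was statistically significant". Section 7.1 repeats it for month 6.

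**The concern.** Objective 2.1 is about the dialysate. A before-after comparison can be read that way only if nothing else that raises albumin or prealbumin is started because of how the patient is doing. Section 5.1.2 permits exactly that, in the patients whose primary endpoint is falling, and a scheduled month-3 result leaves about three months for support to act before the month-6 sample. No comparison group receives the same support, and 7.6.2 makes no use of the concomitant-treatment record. Any gain from support would therefore enter the month-6 mean and be reported as dialysate effect. Because the support is undefined, two of the five centres could both follow the protocol and treat the same patient differently.

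The extra amino acid exchanges are a separate matter. They are the study product, so with them month 6 still describes an adjustable dose of it.

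**Working it through.** **1. The texts side by side.** Section 5.1.2 names the dialysate increase separately, so support means something more. Section 1 lists oral, enteral and parenteral supplementation as the main alternatives to modified dialysate. Section 4.1 already gives every subject dietary guidance. Reading A: support includes supplements; 5.1.2 then permits what 5.2 excludes. Reading B: support is food or counselling; 5.2 is not breached. On both readings a fall in a primary endpoint starts a second treatment.

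**2. The plan's own figures (7.1).** One-sided α = 0.0125, power 0.90, n = [(2.241 + 1.282) × SD/δ]².
- Albumin, δ = 1.5 and SD = 4.5 g/L: 111.7, so 112.
- Prealbumin, δ = 60 and SD = 80 mg/L: 22.06, so 23.
- With 20% dropout: 112/0.8 = 140.

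All three reproduce and are not in dispute. (The formula as displayed lacks the square on the z sum; the stated sizes need it.)

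**3. How often the trigger could be met.** Assume 4.5 g/L is the SD of change at months 3 and 6.
- No dialysate effect: P(any albumin fall at month 3) = 0.50; P(fall above 2 g/L) = Φ(−2/4.5) = 0.328; P(albumin or prealbumin falls) = 0.75 if the two changes are uncorrelated, 0.667 if their correlation is 0.5.
- Effect of 1.5 g/L already at month 3: P(any albumin fall) = Φ(−1.5/4.5) = 0.37.

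**4. False-positive rate of the albumin test, no dialysate effect, n = 112.** SE = 4.5/√112 = 0.425. Significance needs a mean rise of 2.241 × 0.425 = 0.95 g/L (0.97 with the t distribution). Approximately, P(significant) = Φ(share × gain/0.425 − 2.241), where share is the fraction of patients supported and gain is what support adds to each.

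| Who is supported | Share | Gain 0.25 g/L | Gain 0.75 g/L | Gain 1.5 g/L |
|---|---|---|---|---|
| Half of falls above 2 g/L | 0.164 | 1.6% | 2.5% | 4.8% |
| Half of all falls | 0.25 | 1.8% | 3.6% | 8.7% |
| Every fall | 0.50 | 2.6% | 8.7% | 32% |

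Simulating the paired t-test (20,000 runs per case, month 3–6 correlation 0.3 to 0.7) agrees closely, except that the bottom-right cell becomes 33 to 37%. With no support it gives the nominal rate, 1.2 to 1.3%. Share and gain are assumptions in every cell.

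**5. If the dialysate works as planned (1.5 g/L at both visits).** Half of falls above 2 g/L is 0.5 × Φ(−3.5/4.5) = 0.109 of patients. At a gain of 0.25 the reported mean is 1.5 + 0.109 × 0.25 = 1.53 g/L. With every fall supported and a gain of 1.5 it is 1.5 + 0.37 × 1.5 = 2.05 g/L.

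**6. Which analysis removes the support effect.** In the same no-effect runs:
- carrying forward the value that triggered support shifts the mean by −0.24 to −1.26 g/L;
- excluding supported patients shifts it by +0.29 to +2.5 g/L;
- regression imputation from month 3 is unbiased when month 3 alone triggers support.

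If an unscheduled later value triggers it (assumed month 5; correlations 0.5 for months 3–5, 0.7 for 5–6, 0.4 for 3–6; half of falls supported), month-3-only imputation is biased by about +0.6 g/L. Adding the triggering value to the imputation brings the bias to about zero, provided that the later value is available for all patients.

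**The case against.** The best defence is that the sections can be read together: 5.2 is the specific rule and excludes new drugs, while 5.1.2 pairs support with education and so may mean diet and counselling. The text is plainly a translation, and a contradiction that turns on support versus support drugs is fragile. This stands, and it is why the conflict with 5.2 is conditional. It does not remove the concern, because reading B still starts a second treatment after a fall in a primary endpoint.

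On reading B the gain may be small. At 0.25 g/L the error rate moves only from 1.25% to between 1.6 and 2.6%. That also stands.

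A reader might infer more than the documents support:
- **5.1.2 flatly contradicts 5.3.** Section 5.3 addresses participants and also tells them to follow dietary advice. The tension is one of intent.
- **7.6.2 credits the change to the dialysate.** It only specifies a test; the effectiveness rule is in 3.2.1 and 7.1.
- **Non-drug support would go unrecorded.** The Table 1 row covers combination therapy as well as medication, and 7.6.1 summarises treatment categories. What is missing is any use of these data in the efficacy analysis.
- **The trial has a one-in-three chance of a false claim.** That needs every fall, however small, to be supported, although 5.1.2 says only that the investigator can act. It also needs each supported patient to gain the full 1.5 g/L that 7.1 assumes for the dialysate itself. The figures also concern the albumin test at 0.0125 alone. Success under 7.7 is either endpoint under Hochberg, and no trial-level rate is calculated here.

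**Conclusion.** The point holds in this form: a fall in a primary endpoint may start undefined nutritional support, and neither the design nor the planned analysis can tell its effect from that of the dialysate. The breach of 5.2 depends on support including supplements; the attribution problem does not.

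The documents do not fix the size. Under the stated assumptions, the albumin test's error runs from barely above nominal (1.6%) through 9% in the middle cases to about a third at an upper extreme. If no support is started, the bias is zero. The change should be made because it is cheap and because section 1 presents the study as an answer to low-quality evidence. Confidence is moderate, since uptake and gain are unknown.

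**What to change.** **5.1.2:** replace the closing clause on support and education with: *and repeat the dietary guidance given to all patients; as in 5.2, no oral, enteral or parenteral nutritional product is started or increased before the month-6 sample unless clinically necessary, in which case product, dose, start date and reason are recorded under concomitant therapy.*

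**5.2:** extend the restriction on nutritional support drugs with *or other nutritional products*, with the same exception.

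**7.6.2:** keep the primary test in all EAS patients and report how many received new support. Add a sensitivity analysis: *Values taken after newly started nutritional support are treated as missing and multiply imputed from all albumin and prealbumin values before its start, including any unscheduled value that triggered it; neither LOCF nor exclusion is used for these values. Both estimates are reported with confidence intervals.*

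**Cost:** wording in three sections and one analysis. The sample size does not change, and patients who need supplements still receive them. Some centre discretion remains through the clinical exception, but it becomes visible. The sensitivity interval is wider: in the simulations the standard error rises from 0.42 to about 0.5 g/L if half of falls are supported, and to 0.8–1.0 if every fall is, when the imputation also rests on extrapolation. The analysis depends on the triggering values being recorded.

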5.2 Adjuvant therapy/combined medication

During treatment, in addition to the use of amino acid peritoneal dialysis fluid and glucose peritoneal dialysis fluid, the subjects should also

Continue with their original adjuvant therapy, including:

Nutritional support drugs: if the patient has been taking nutritional drugs before entering the study, continue the original nutritional drug treatment,

No additional nutritional support drugs were added after entering the study.

Antihypertensive drugs: adjust the type of antihypertensive drugs according to the patient's blood pressure level and ultrafiltration. The dose is used to keep blood pressure within the target range.

Antianemia drugs: erythropoietin is adjusted according to the patient's hemoglobin level and iron metabolism. The type and dose of EPO and iron supplements were used to improve anemia.

Calcium and vitamin D drugs: according to the patient's blood calcium, blood phosphorus, parathyroid hormone (PTH) and other indicators

Targets, adjust the types and doses of calcium and vitamin D drugs to prevent and treat renal bone disease.

Phosphorus binder: Adjust the type and dose of phosphorus binder according to the patient's blood phosphorus level and diet. Control blood phosphorus levels within the target range.

Anticoagulant drugs: adjust the type and dose of anticoagulant drugs according to the patient's coagulation function to prevent and treat thrombosis.

Other drugs: other necessary drug therapy, such as anti-infective drugs, is given according to the specific condition of the patient anti-heart failure drugs, anti-arrhythmia drugs, uric acid reduction.

5.3 Treatment compliance

During the treatment period, participants should use the amino acid peritoneal dialysate and glucose peritoneal dialysate correctly according to the instructions and prescriptions of the researcher, and record each infusion volume, retention time, and output. Participants should submit their daily treatment logs to the researcher for verification and storage. Participants should maintain good peritoneal dialysis techniques and hygiene habits to prevent infections and complications. Participants should regularly visit the research center for follow-up visits and examinations, and promptly report any adverse reactions or discomforts to the researcher. Participants should adhere to dietary, hydration, and exercise recommendations provided by the researcher and avoid using other drugs or treatments that may affect the results of this study. If a participant is unable to continue participating in this study for any reason, they should notify the researcher in a timely manner and explain the reasons for withdrawal follow.

6. Adverse events

6.1 Definition of adverse events

Adverse events (Adverse Event, AE) are any harmful medical events that occur during a clinical trial. Events, regardless of whether they have a causal relationship with the test drug. Adverse events include the following: Adverse reactions related to the test drug (Adverse Reaction, AR): refers to the normal use conditions. Any harmful medical event caused by the pharmacological action of the test drug or for other reasons. Adverse events not related to the test drug: any harmful medical event that occurs during a clinical

trial, However, it was scientifically determined that there was no causal relationship with the test drug.

Serious adverse events (Serious Adverse Event, SAE): refers to those that occur during clinical trials

Any harmful medical event, regardless of whether it has a causal relationship with the investigational drug, that results in one of the following outcomes:

Causing death;

Life-threatening (i.e., potentially fatal if not promptly intervened);

Hospitalization or extension of hospitalization is required;

Causing permanent or significant disability or impairment;

Causing congenital malformations or birth defects;

Major medical intervention (such as surgery, blood transfusion, etc.) is required.

